7.3 Lost to Follow-up

A participant will be considered lost to follow-up if he repeatedly fails to return for scheduled visits and cannot be contacted by the study site.

The following actions must be taken if a participant fails to return to the clinic for a required study visit:

- The site must attempt to contact the participant and reschedule the missed visit as soon as possible. The site should counsel the participant on the importance of maintaining the assigned visit schedule and ascertain whether or not the participant wishes to and/or should continue in the study.
- Before a participant is deemed lost to follow-up, the investigator or designee must make every effort to regain contact with the participant (where possible, three telephone calls and, if necessary, two certified letters to the participant's last known mailing address or local equivalent methods). These contact attempts should be documented in the participant's medical record.
- Should the participant continue to be unreachable, he will be considered to have withdrawn from the study.
- Site personnel, or an independent third party, will attempt to collect the vital status of the participant within legal and ethical boundaries for all participants randomised, including those who did not receive study intervention. Public sources may be searched for vital status information. If vital status is determined as deceased, this will be documented and the participant will not be considered lost to follow-up. Sponsor personnel will not be involved in any attempts to collect vital status information.

Discontinuation of specific sites or of the study as a whole is handled as part of Appendix 10.1 (Section 10.1).

8 STUDY ASSESSMENTS AND PROCEDURES

- Study procedures and their timing are summarized in the SoA. Protocol waivers and exemptions are not allowed.
- Immediate safety concerns should be discussed with the sponsor immediately upon occurrence or awareness to determine if the participant should continue or discontinue study participation.
- Adherence to the study design requirements, including those specified in the SoA, is essential and required for study conduct.
- All screening evaluations must be completed and reviewed to confirm that potential participants meet all eligibility criteria. The investigator will maintain a screening log to record details of all participants screened and to confirm eligibility or to record reasons for screening failure, as applicable.
- Procedures conducted as part of the participant's routine clinical management (e.g. blood count) and obtained before signing of the ICF may be utilised for screening or baseline purposes provided the procedures met the protocol-specified criteria and were performed within the timeframe defined in the SoA.
- The maximum amount of blood collected from each participant over the duration of the study, including any extra assessments that may be required, will not exceed 12 mL.
- Repeat or unscheduled samples may be taken for safety reasons or in case of technical issues with the samples.

8.1 Efficacy/Pharmacodynamic Assessments

[figure not shown]
Planned timepoints for all pharmacodynamic assessments are provided in the SoA (see Section 1.3).

8.1.1 Compound Muscle Action Potential

The CMAP procedure will be performed on the injected foot by a neurophysiologist (different from the study intervention injector) at the study centre.

The effect in the EDB injected muscles will be quantified by the electrophysiologic evaluation of the CMAP peak-to-peak total amplitude (mV), elicited by supramaximal electrical stimulation of the peroneal nerve at the ankle. Latency for the M wave will also be collected (Figure 2).

Figure 2 Compound Muscle Action Potential

Surface electrodes will be used as recording electrodes (placed over the muscle belly) and reference electrodes (placed over the tendon of the corresponding muscle). The point of maximum response of both EDB, as assessed during the screening period will be marked with indelible ink to allow recording from the same site on subsequent occasions.

At each visit (including the screening visit), three measurements of CMAP will be carried out at approximately 2-minute intervals. The three values of CMAP recorded will be averaged to calculate the corresponding visit value.

The intensity in mA required to cause supramaximal stimulation should be recorded for each CMAP assessments throughout the study.

Surface skin temperature of the injected foot will be recorded and ascertained to be above 32°C prior to each CMAP test.

8.2 Safety Assessments

Planned time points for all safety assessments are provided in the SoA (see Section 1.3).

8.2.1 Physical Examinations

A complete physical examination will include, at a minimum, assessments of the cardiovascular, respiratory, gastrointestinal and neurological systems. Height and weight will also be measured and recorded at Visit 1 only. The investigator should pay special attention to clinical signs related to previous serious illnesses.

8.2.2 Vital Signs

Vital signs (systolic and diastolic blood pressures and heart rate) will be recorded during the study. Vital signs will be measured with the participant standing and in a supine position after resting for 3 minutes. At Baseline (Day 1), vital signs will be recorded before treatment.

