1.3 Schedule of Activities (SoA)

The schedule of study procedures and assessments are summarised in [Table 1](#).

If the coronavirus disease 2019 (COVID-19) pandemic prevents participants from coming to the site, participants can have their study visit assessments performed remotely as judged appropriate by the investigator. This must be discussed with the sponsor before being implemented. In such a case, the investigator will perform a telemedicine visit and will make every effort, where applicable, to contact (subject to consent) the participant's general practitioner or specialist physician to ensure all important medical information and safety event(s) occurring since the last visit are collected. Guidance on how to collect protocol planned assessments will be provided to the investigator in a separate document. Such document will be filed in the trial master file. Independent ethics committees (IECs)/institutional review boards (IRBs) will be notified of the changes as applicable locally. Of note, as the adapted visit deviates from the regular protocol plan, the changes will be recorded as protocol deviations related to COVID-19.

Table 1 Schedule of Activities

Procedure	SCR	BSL	Double-blind Period										EoS /EW	Notes
Visit	Visit 1	Visit 2	Visit 3	Visit 4	Visit 5	Visit 6	Visit 7	Visit 8	Visit 9	Visit 10	Visit 11	Visit 12	Visit 13	
Scheduled Day/Week	Day -14 to Day -1	Day 1	Day 7	W4	W8	W12	W16	W20	W24	W28	W32	W36	W40	
Visit window (days)	-	-	±1 day	± 3 days		± 6 days								
Informed consent	X													
Inclusion and exclusion criteria	X	X												
Demography	X													
Body weight and height	X													
Medical history and surgical history	X													
Alcohol breath test/Drug test	X	X												
Randomisation		X												
Study intervention administration		X												
Physical examination	X	X											X	

Procedure	SCR	BSL	Double-blind Period											EoS /EW	Notes
Visit	Visit 1	Visit 2	Visit 3	Visit 4	Visit 5	Visit 6	Visit 7	Visit 8	Visit 9	Visit 10	Visit 11	Visit 12	Visit 13		
Scheduled Day/Week	Day -14 to Day -1	Day 1	Day 7	W4	W8	W12	W16	W20	W24	W28	W32	W36	W40		
Vital signs	X	X												X	Standing and supine blood pressures and heart rate. Measurements to be taken prior to sampling for laboratory tests where possible.
12-lead ECG	X														
Clinical laboratory tests	X														Haematology, blood chemistry, coagulation and serology

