2.2 Benefit/Risk Assessment

This study will be conducted in healthy male participants. There is no benefit for this study population.

Risks inherent to the administration of BoNT are those related to distant spread from the site of administration. In clinical practice, the risk of occurrence of such undesirable effects may be reduced by using the lowest effective possible dose and by not exceeding the maximum recommended dose per indication as indicated in the respective product labels. Doses that will be investigated in the present study have been shown to safe and well tolerated, also associated with a lack of local diffusion to the adjacent muscles [[Pons 2019](#), [Wohlfarth 2007](#)].

There have also been occasional reports of hypersensitivity. This potential risk will be mitigated by appropriate selection of participants.

More detailed information about the known risks and reasonably expected adverse events may be found in the respective product labels for Dysport, Botox and Xeomin.

Safety will be closely monitored during the study. Type, severity, seriousness, duration, reversibility and outcome of treatment-emergent AEs (TEAEs) and adverse events of special interest (AESIs), a well as TEAEs leading to withdrawals will be followed. In addition, all AEs will be monitored by the sponsor to determine if they meet the criteria of AESIs.

2.2.1 *Risk Assessment of the Impact of COVID-19 Vaccination on Study Participants*

Currently there is no evidence of an increased safety risk in patients treated with BoNT prior to or following vaccination against COVID-19.

The doses of study intervention (BoNT) to be used in the study have been shown to be safe when injected into the EDB muscle. At 40 U, there is no local diffusion of Dysport into adjacent muscles. However, as a precautionary measure and to help minimise confounding factors in the safety assessments, a COVID-19 vaccine should not be administered within 7 days before or after the study intervention injection.

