4.2 Scientific Rationale for Study Design

The higher quantity of neurotoxin in Dysport than Botox or Xeomin at the approved FDA dose used in therapeutic and aesthetic indications may contribute to the prolonged duration of action exhibited by Dysport compared with other BoNT-A products [[Field 2018](#)]. Using the same dose ratio, this study aims to demonstrate a longer duration of action of Dysport compared to Botox and Xeomin in a well-known and recognized pharmacodynamic model in healthy male participants.

This model uses the EDB muscle and records its compound muscle action potential (CMAP) following supramaximal stimulation of the corresponding nerve. The present design will capture the CMAP of injected EDB with either Dysport, Botox or Xeomin. The expected inhibition of the electrophysiological signal following BoNT administration will be followed in parallel study intervention groups and blinded conditions, up to 40 weeks after injection aiming at capturing recovery of the inhibition.

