5.8.4 Vital Signs

A summary of the actual and change from baseline in each vital signs parameter by study intervention group and timepoint will be performed as well as a listing of vital sign data by study intervention group, with abnormal value highlighted. A listing of participants with Potentially Clinically Significant Abnormalities (PCSA) values as defined in [Appendix A5](#) will also be prepared. All data for a vital signs parameter will be displayed for a participant having at least one post-baseline PSCA value.

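### Completers have no scheduled vital signs or physical examination between Day 1 and Week 40, so the planned vital-sign outputs cannot show a transient change after injection

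*Protocol*

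**What the plan says.** Protocol section 8.2 leaves the timing of safety assessments to the schedule: "Planned time points for all safety assessments are provided in the SoA (see Section 1.3"). In Table 1 the vital-signs row begins "Vital signs X X" (screening and Day 1) and is then blank until the final end-of-study/early-withdrawal column. The physical-examination row has the same pattern. Section 8.2.2 adds no visits and fixes the order on Day 1: "At Baseline (Day 1), vital signs will be recorded before treatment".

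The 12-lead ECG (section 8.2.3) and the safety laboratory tests (Appendix 2, Table 4) are done at screening only, apart from SARS-CoV-2 testing. Adverse events and concomitant medications are recorded at every visit.

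For the analysis, SAP 5.8.4 states: "A summary of the actual and change from baseline in each vital signs parameter by study intervention group and timepoint will be performed". It also plans a listing of participants with potentially clinically significant abnormalities (PCSA), using the limits in Appendix A5. SAP 5.8.5 plans a normal/abnormal shift in the physical examination from baseline to the end-of-study visit. SAP 6.2 restricts by-visit tables to scheduled visits, and for those tables moves an early-withdrawal visit to the participant's next empty visit number.

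Protocol Appendix 4 includes bradycardia among the events suggesting remote spread of toxin, and areflexia and hyporeflexia under muscle function.

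**The concern.** Participants receive one injection and are then followed "up to 40 weeks after injection aiming at capturing recovery of the inhibition". The scheduled blood pressure, heart rate and examination come only before the injection and at the end of that follow-up. In between lie onset, maximal effect and the period around six months at which section 4.3 reports remaining inhibition with Dysport 40 U.

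A temporary change in heart rate or blood pressure that has resolved by Week 40 leaves no trace in the scheduled data of a completer. A Week 40 table with little change could then be read as reassurance about months in which nothing was scheduled to be measured.

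The adverse-event route does not fully close the gap. Section 8.3.2 prefers open, non-leading questions, which find symptoms rather than symptomless signs. Section 10.3.1 counts a worsened vital sign as an adverse event if the investigator judges it clinically significant, but someone must first measure it. If bradycardia is first seen at Week 40, its onset is unknown, and SAP 5.8.3 allows a potential remote-spread event to be excluded when its timing does not fit the expected mechanism.

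**Working it through.** The check is a count from the schedule. The plan states no figure for it.

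**Inputs**
- Visits after injection (Protocol synopsis and Table 1): Day 7 and Weeks 4, 8, 12, 16, 20, 24, 28, 32, 36 and 40.
- Visits after Day 1 with vital signs or physical examination marked (Table 1): Week 40, or early withdrawal.
- Visit window for the later visits (Table 1): ±6 days.
- Planned sample (Protocol 9.2): 45 participants, 15 per group.

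**Coverage for a completer**
- Post-dose visits: 1 + 10 = 11.
- With scheduled vital signs: 1/11 = 9.1%.
- Day 7 to Week 36: 0 of 10 visits.
- First scheduled post-dose value: 40 × 7 = 280 days after injection, or 274 to 286 days within the window; 280/30.4375 = 9.2 months.

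**What the planned outputs can contain**
1. *Change from baseline by timepoint (SAP 5.8.4).* For completers there is one post-dose timepoint, Week 40. Any interim row could hold only reassigned early-withdrawal visits under SAP 6.2, hence no completers.
2. *PCSA listing (SAP 5.8.4, Appendix A5).* Each completer contributes one scheduled post-dose session (standing and supine readings). Unscheduled values also reach the listings but depend on someone deciding to measure.
3. *Examination shift (SAP 5.8.5).* One post-dose assessment, at the end-of-study visit. The SAP does not say whether an early-withdrawal examination counts as that visit.
4. *Weight criterion (Appendix A5).* A5 sets a limit of 5% change from baseline in either direction, but Protocol 8.2.1 says: "Height and weight will also be measured and recorded at Visit 1 only". No scheduled data can fill this row.

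**Other scheduled measurements that might fill the gap.** None: ECG is at screening only, and so are the laboratory tests apart from SARS-CoV-2.

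**After the proposed change**
- Coverage for vital signs: 3/11 = 27.3%, with the first post-dose value at Day 7 instead of about day 280.
- Added measurement sets: 2 × 45 = 90 if nobody withdraws.

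**The case against.** The strongest reply is that this is a choice about monitoring density, not an error. Vital signs and examinations are not endpoints: the safety endpoints in Protocol Table 2 are adverse events, serious events, events leading to withdrawal, and events of special interest. All of these are collected throughout. Section 10.3.3 obliges the investigator to arrange further measurements when medically indicated, and potential remote-spread events are medically evaluated before unblinding. The protocol describes the doses as already shown to be safe in this muscle. Much of this stands, and it is why the point is minor. It does not answer the symptomless sign, which prompts neither a complaint nor an extra measurement.

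A reader might infer more than the documents support:

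- *That the SAP contradicts the schedule.* It does not. A summary by timepoint is satisfied by whatever timepoints are scheduled, and the examination shift is defined to the visit at which the examination is done.
- *That safety goes unwatched, against the statement "Safety will be closely monitored during the study".* The sentences after it explain the monitoring in terms of adverse events and events of special interest, not serial vital signs.
- *That the toxin is inactive at Week 40, so the late reading is worthless.* The documents do not say so. Amplitude and recovery at Week 40 are alpha-controlled secondary endpoints, so some residual effect is possible.
- *That the tables would show no change whatever the products did.* This is not shown. They cannot reveal a change that has resolved by Week 40; a persistent one could still appear.
- *That bradycardia is expected here.* Its presence on a list of terms is not evidence that it will occur.
- *That early-withdrawal values contaminate the Week 40 row.* SAP 6.2 keeps most of them out.

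**Conclusion.** The concern holds in a limited form. For completers, no vital signs or physical examination are scheduled between the Day 1 assessment and Week 40: 0 of 10 visits, with the first post-dose value at about 280 days. The SAP 5.8.4 outputs therefore cannot show whether a transient heart-rate or blood-pressure change occurred during onset, maximal effect or the residual inhibition reported at six months. A symptomless listed sign such as bradycardia would not be measured on schedule in that time.

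This rests on Table 1 being the complete schedule, as section 8.2 says. It also treats the Day 1 examination as a baseline value: the pre-dose order is explicit for vital signs, while for the examination it follows from the baseline column of Table 1 and the SAP 5.1.3 baseline definition.

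The documents give no rate for transient vital-sign changes at these doses, so the number of events that might be missed cannot be estimated. No pharmacodynamic result is affected. This is an inexpensive improvement to the safety objective, not a defect that undermines the trial.

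**What to change.** **Main change.** In Protocol Table 1 and section 8.2.2, add blood pressure and heart rate at the existing Day 7 and Week 4 visits, and keep the end-of-study/early-withdrawal set. Add both timepoints to SAP 5.8.4.

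The cost is a few minutes per participant at each of two visits already attended, with no new staff or equipment, plus amended wording. The documents give no time window for systemic effects; Day 7 and Week 4 are simply the two earliest existing visits. The change leaves the physical-examination gap as it is, so reflex signs would still depend on examinations prompted by an adverse event.

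**Do not move the Week 40 set to an earlier visit.** That would lose the exit reading. Because end of study and early withdrawal share one column in Table 1, it could also remove the withdrawal reading, although section 7.2 asks for a complete final evaluation at withdrawal.

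**Minor clean-up, wording only.** Remove the weight row from SAP Appendix A5, which changes no result. State in SAP 5.8.5 whether an early-withdrawal examination counts as the end-of-study visit.

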8.2.3 Electrocardiograms

A 12-lead ECG will be recorded at a paper speed of 25 mm/sec at Visit 1 with the participant in a supine position after 5 minutes of rest.

8.2.4 Clinical Safety Laboratory Assessments

- See Appendix 10.2 for the list of clinical laboratory tests to be performed and to the SoA (Section 1.3) for the timing and frequency.
- The investigator must review the laboratory report, document this review, and record any clinically significant changes occurring during the study as an AE. The laboratory reports must be filed with the source documents.
- All laboratory tests with values considered clinically significantly abnormal during participation in the study should be repeated until the values return to normal or baseline or are no longer considered clinically significant by the investigator or medical monitor.
- If clinically significant/any values do not return to normal/baseline within a period of time judged reasonable by the investigator, the aetiology should be identified and the sponsor notified.
- All protocol-required laboratory tests, as defined in Appendix 10.2, must be conducted in accordance with the SoA (Section 1.3).
- If laboratory values from non-protocol specified laboratory tests performed at the institution's local laboratory require a change in participant management or are considered clinically significant by the investigator (e.g. SAE or AE or dose modification), then the results must be recorded in the eCRF.

8.2.5 *SARS-CoV-2 Testing*

SARS-CoV-2 testing will be performed as outlined in the SoA (Section 1.3). Prior to the Screening visit, potential participants will be contacted by telephone and instructed not to visit the study site for at least 14 days if they have COVID-19 symptoms, have been in close contact with a positive individual, or have tested positive with COVID-19 following a SARS-CoV-2 test in the last 2 weeks. At the Screening visit, participants will be scheduled at least 5 minutes apart from one another to lessen the likelihood of infection spread. Participants will have a swab of the nose or back of the throat tested for COVID-19 infection using reverse transcription polymerase chain reaction (PCR).

Only participants who have a negative COVID-19 test at Screening will be allowed to attend the study site on Day 1 for study intervention administration. At the Baseline visit on Day 1, participants will be re-tested using a rapid SARS-CoV-2 antigen test (approximately 15 minutes) and confirmed negative prior to injection of the study intervention.

The investigator may request a participant be re-tested at any time during the study if required or in the event of suspected COVID-19 infection using PCR.

8.3 Adverse Events (AEs) and Serious Adverse Events (SAEs), and Other Safety Reporting

The definitions of adverse events (AEs) and serious adverse events (SAEs) can be found in Appendix 10.3.

Adverse events will be reported by the participant (or, when appropriate, by a caregiver, surrogate, or the participant's legally authorised representative).

The investigator and any qualified designees are responsible for detecting, documenting, and recording events that meet the definition of an AE or SAE and remain responsible for following up all AEs (see Section 7).

The method of recording, evaluating, and assessing causality of AEs and SAEs and the procedures for completing and transmitting SAE reports are provided in Appendix 10.3.

8.3.1 *Time Period and Frequency for Collecting AE and SAE Information*

All AEs/SAEs will be collected from the signing of the ICF until EoS/EW visit at the time points specified in the SoA (Section 1.3).

Medical occurrences that begin before the start of study intervention but after obtaining informed consent will be recorded on the AE section of the case report form.

All SAEs will be recorded and reported to the sponsor or designee immediately and under no circumstance should this exceed 24 hours of awareness of the event, as indicated in Appendix 10.3. The investigator will submit any updated SAE data to the sponsor within 24 hours of it being available.

Investigators are not obligated to actively seek information on AEs or SAEs after conclusion of the study participation. However, if the investigator learns of any SAE, including a death, at any time after a participant has been discharged from the study, and he/she considers the event to be reasonably related to the study intervention or study participation, the investigator must promptly notify the sponsor.

8.3.2 *Method of Detecting AEs and SAEs*

Care will be taken not to introduce bias when detecting AEs and/or SAEs. Open-ended and non-leading verbal questioning of the participant is the preferred method to inquire about AE occurrences.

8.3.3 *Follow-up of AEs and SAEs*

After the initial AE/SAE report, the investigator is required to proactively follow each participant at subsequent visits/contacts. All SAEs, and AEs of special interest (as defined in Section 8.3.6), will be followed until resolution, stabilisation, the event is otherwise explained or the participant is lost to follow-up (as defined in Section 7.3). Further information on follow-up procedures is provided in Appendix 10.3.

8.3.4 *Regulatory Reporting Requirements for SAEs*

- Prompt notification by the investigator to the sponsor of an SAE is essential so that legal obligations and ethical responsibilities towards the safety of participants and the safety of a study intervention under clinical investigation are met.
- The sponsor has a legal responsibility to notify both the local regulatory authority and other regulatory agencies about the safety of a study intervention under clinical investigation. The sponsor will comply with country-specific regulatory requirements relating to safety reporting to the regulatory authority, Institutional Review Boards (IRB)/Independent Ethics Committees (IEC), and investigators.
- An investigator who receives an investigator safety report describing an SAE or other specific safety information (e.g. summary or listing of SAEs) from the sponsor will review and then file it along with the package insert and will notify the IRB/IEC, if appropriate according to local requirements.
- Investigator safety reports must be prepared for suspected unexpected serious adverse reactions (SUSAR) according to local regulatory requirements and sponsor policy and forwarded to investigators as necessary.

8.3.5 *Pregnancy*

- Details of all pregnancies in female partners of male participants will be collected from the signing of the ICF and until completion of the study and within 90 days after the participants last dose of study intervention or completion of the study (whichever is greater).
- If a pregnancy is reported, the investigator will record pregnancy information on the appropriate forms (SAE form in the eCRF and Drug Exposure Form – paper form) and submit it to the sponsor within 24 hours of learning of the female partner of male participant pregnancy (after obtaining the necessary signed informed consent from the female partner).
- Any pregnancy complication or elective termination of a pregnancy for medical reasons will be reported as an AE or SAE.
- Abnormal pregnancy outcomes (e.g. spontaneous abortion, fetal death, stillbirth, congenital anomalies, ectopic pregnancy) are considered SAEs and will be reported as such.
- The pregnant female partner will be followed to determine the outcome of the pregnancy. The investigator will collect follow-up information on the pregnant female partner and the neonate and the information will be forwarded to the sponsor.
- Any post-study pregnancy-related SAE considered reasonably related to the study intervention by the investigator will be reported to the sponsor as described in Section 8.3.4. While the investigator is not obligated to actively seek this information in former study pregnant female partners, he or she may learn of an SAE through spontaneous reporting.

